4.3 Intervention

The antibiotic used will be rifaximin. Rifaximin acts by inhibition of bacteria synthesis of RNA. It is active against gram positive and gram negative bacteria including both aerobes and anaerobes however it is not absorbed in the gastro-intestinal system facilitating its use in enteric infections. It is licensed for the treatment of acute bacterial diarrhea and SIBO. [21] We have chosen to use rifaximin over metronidazole because it is not enterically absorbed and as such has less of a side-effect profile. Metronidazole causes a higher incidence of nausea and GI upset, has a greater amount of drug interactions and it also has a metallic taste which could effect blinding and introduce bias.

For this trial, both rifaximin and placebo will be prepared in identical capsules by the research pharmacist at MSKCC and distributed to the outpatient pharmacies. We have chosen a rifaximin dose of 400 mg bid for 4 weeks as this has been shown to be efficacious in the treatment of SIBO at this dose over 14 days. We have added a further

2 weeks to the treatment regime as from prior experience by the PI's using rifaximin in this condition, the beneficial effect tends to reduce over one week. As the BFI is validated for use over a 4 week period (ie assessing bowel function over a 4 week period), to show an effect on bowel function as assessed by the BFI, treatment is needed over a four week period. We plan to assess bowel function at 4 weeks after the completion of treatment to determine if the response to treatment is transient or whether it is a more durable effect. Following the completion of the trial patients will be offered a 3 week treatment with 500 mg of metronidazole tid. They will be assessed with the BFI at pretreatment and again at 0-1 and 4-6 weeks post treatment. Should the effect be transient, this will lead to future studies to assess if adding extra treatment with other medications such as pro-biotics may prolong the effect.

5.1 THERAPEUTIC/DIAGNOSTIC AGENTS

5.2 Rifaximin (Xifaxan®)

Rifaximin is a non-aminoglycoside semi-synthetic, nonsystemic antibiotic derived from rifamycin SV with a chemical name of 5,6,21,23,25- pentahydroxy-27-methoxy-2,4,11,16,20,22,24,26-octamethyl-2,7(epoxypentadeca-[1,11,13]trienimino)benzofuro[4,5-e]pyrido[1,2- α]-benzimidazole-1,15(2H)dione, 25-acetate. It comes in preparations of 200mg and 550mg tablets. It can be stored at room temperature and is FDA licensed for use in the treatment of bacterial intestinal infections.

5.3 Metronidazole (Flagyl®)

Metronidazole is an oral synthetic antiprotozoal and antimicrobial agent with a chemical name of 1-(β -hydroxy-ethyl)-2-methyl-5-nitroimidazole. It comes in oral preparations of 250mgs and 500mgs tablets. It can be stored at room temperature and is FDA licensed for the treatment of bacterial intestinal infections.

6.1 CRITERIA FOR SUBJECT ELIGIBILITY

6.2 Subject Inclusion Criteria

- Patients with a history of rectal cancer treated with an anterior resection preformed at MSKCC (tumor at or below 12cm from anal verge) with restoration of bowel continuity ≥ 1 and ≤ 5 years. (Patients may also have had

procedures to construct neo-rectums including j-pouch, coloplasty, and end to side anastomosis).

- Patients \geq 21 years of age.
- Presence of anterior resection symptoms by patients own assessment. These symptoms may include any of the following: incomplete evacuation, clustering of bowel motions, frequency of bowel motions, unformed stool, excessive flatus, or incontinence of flatus and/or feces.

6.3 Subject Exclusion Criteria

- Local recurrence of rectal cancer.
- Antibiotic treatment within the last 4 weeks for any condition.
- Pregnancy or breast feeding.

7.0 RECRUITMENT PLAN

Patients who have had an anterior resection for rectal cancer at MSKCC will be identified from a prospective database maintained by the Colorectal Surgery Service. These patients will be contacted by a letter inviting them to participate in a randomized study designed to evaluate the beneficial effects of rifaximin and placebo on bowel function. **Appendix 1.** We will ask patients to participate in the trial based on their own personal perception of their symptoms. Patients will be asked in the letter to contact [name] (PI) or [name] (Research Fellow) by email, telephone, or letter. Patients who have not responded to the letter after one month will be contacted by phone and invited to participate. **Appendix 4.** Every attempt will be made to recruit women and minorities to participate in this study. Participation is voluntary. Patients who are interested in participating will be scheduled for a research clinic visit with [name] or another of the consenting professionals. Consenting patients will be registered and randomized at the initial clinic visit. We hope to recruit 70 patients, 35 in each arm in an attempt to have at least 30 patients per arm for analysis allowing for patient dropout.

Patients will also be asked to volunteer to submit stool samples and breath tests. Those who agree will be tested for stool bacteria and SIBO at the relevant time points along with the MSKCC BFI. For those patients who do not agree to volunteer to supply stool samples and breath test, they will be tested using the MSKCC BFI alone at the relevant time periods. All patients will fill out the stool log/diary. We hope to recruit half of the patients in each arm to participate in the extra testing. We are not testing all patients with stool sampling and breath tests as we feel it will hamper accrual into the trial. Patients will be reimbursed with a \$100 gift card for each outpatient visit to cover transport costs for participating in this trial. Following completion of the phase III portion of the trial, patients will be contacted by phone and offered to participate in a follow up single arm study to assess the efficacy of metronidazole in the treatment of bowel dysfunction.

Memorial Sloan Kettering Cancer Center
[name]
[name]

Patients already enrolled on version A(0) or A(1) will also be asked via phone to participate in the follow up study. If they wish to participate, they will be reconsented. Consent forms will be mailed to them with a self addressed return envelope.

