Appendix 2. Patients will then be invited to undertake a hydrogen breath test and fecal

sampling to assess for bacterial content in their small intestine and stool. Following stratification of patients by the method of anastomosis (stapled or hand sewn), the patients will then be randomized into two groups. The patients will receive treatment with rifaximin or placebo depending on the arm of the trial to which they have been randomized. Patients will at this stage on a volunteer basis be asked to submit stool samples and undertake a breath test. Patients will receive the respective treatment for four weeks. Following cessation of treatment all patients will be assessed using the BFI and respective patients will have repeat stool sampling and breath testing. Patients will then have these tests repeated 4 weeks later. This corresponds to 8 weeks after the start of the trial. For those patients not undertaking stool and breath testing, they will be reminded by phone, mail or email to fill out the BFI. Before and during the trial patients will be asked to fill out a weekly stool diary to evaluate trends on bowel function.

Appendix 3. Both the patients and the physicians will be blinded to the patient treatments. The Initial consultation along with subsequent rounds of testing with submission of stool samples and breath testing will be undertaken by one of the consenting physicians at a specifically arranged and designated “research clinic” at one of MSKCC’s network centers. (Sleepy Hollow, Commack, Main Campus and 53rd St). Patients may also be seen and consented at their regular follow up colorectal clinic visits. At 1 – 24 months after completion of the phase III portion of the trial, patients will be contacted by phone and given the option of receiving metronidazole in a followup, single arm study in which all patients receive the antibiotic. Patients who wish to participate will be mailed a drug prescription for a 3 week course of metronidazole 500mgs tid as well as the BFI forms and stool diary. Pretreatment and posttreatment BFI scores will be collected and analyzed for change in bowel function as was done in the initial Phase III study.

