10.1 EVALUATION DURING TREATMENT/INTERVENTION

Pre-treatment intervention & evaluation all undertaken in an outpatient clinic (day 0)

- MSKCC BFI (for all patients)
- Breath test (for patient volunteers)
- Stool Sampling (for patient volunteers)

Treatment with 400 mg rifaximin bid x 4 weeks or placebo bid x 4 weeks.

Post treatment evaluation at an outpatient clinic, for those patients who volunteered for extra testing. (days 26 - 35 and days 53 – 63)

- MSKCC BFI
- Breath test
- Stool Sampling

Post treatment evaluation for patients not volunteering for extra tests which can be undertaken in the patients home during the following periods. (days 26 - 35 and 53 – 63)

- **MSKCC BFI**

All patients will be required to fill out a weekly stool log/diary for the duration of the trial. There are questions in the log/diary to assess patient compliance also.

One to twenty-four months following completion of the phase III trial patients will be offered a 3 week course of metronidazole. They will then be assessed again using the BFI at pretreatment and at 0-1 and 4-6 weeks post-treatment. (21-30 days and 49 – 63 days following starting metronidazole)

MSKCC BFI

The MSKCC BFI is a validated instrument in the assessment of bowel function following rectal cancer surgery over a 4 week period.[5] It consists of 18 items to which patients respond using a 5-point Likert scale, ranging from Always to Never. There is a summary score, and three subscales with good internal consistency (Frequency ($\alpha=0.75$), Dietary ($\alpha=0.78$), Urgency ($\alpha=0.79$)) and test-retest reliability (total score =0.84, Frequency=0.74, Dietary=0.62, Urgency=0.87). The instrument has demonstrated discriminant and construct validity. It is written at a grade 8 reading level, and takes 5-10 minutes to complete. The BFI if filled out at home can be emailed or mailed back to the investigator where they will be stored on a secure database and a locked drawer. Should there be any incomplete or ambiguous answers a follow up phone call will be made by one of the consenting physicians to clarify the answer. However in a prior trial by the Co-PI ([name] 06-151), of the 125 patients who answered the BFI on multiple occasions less than 5 items per question were missing or filled out inadequately.

Breath Test

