To evaluate the spectrum of fecal bacteria, a PCR plus 454 pyrosequencing technique optimized by one of the Co-Investigators ([name]) will be used. The conserved and variable domains of the gene 16S ribosomal RNA will be amplified as one PCR product using previously described primers. From this product, the variable domain will be analyzed using 454 pyrosequencing technique. Microbial complexity will be determined and comparisons between samples will be performed using UniFrac and Principal Coordinates Analysis. Approximately 120 species of bacteria will be represented in the various Pyrosequencing primers. The read out of the assay will give a positive fluorescent signal for each bacterial species present in the feces.

Expertise in both quantifying total bacterial load and identifying fecal colonization patterns will be provided by [name] and his laboratory.[24]

Stool Diary/Log

The stool diary/log will allow the investigators to follow trends in bowel function and to assess how long the antibiotic effect lasts. Patients will be asked to fill the diary out once per week (+/- 2 days) on paper or by email before and through the duration of the trial. The questions asked will address range of stools per day, stool formation, flatus, incontinence, ability to completely evacuate. Patient compliance will also be assessed in the log. It will not take longer than 3 minutes to fill out. Once the log is completed it can be posted or emailed back to the investigator where it will be stored on a secure database and a locked drawer.

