17.1 PROTECTION OF HUMAN SUBJECTS

Patient wellbeing will always take precedence in this trial however there will be minimal patient risk during this trial. Adverse drug reactions will be the most significant risk to patient health; however rifaximin carries minimal side effects. Should patients develop grade 3 or 4 toxicity to the antibiotic treatment, their treatment will be stopped and they will be removed from the study. The patient will be responsible for all costs related to treatments and complications of treatment except the antibiotic treatment, the placebo, breath testing and stool sampling which will be provided by MSKCC. Participation in this clinical trial is voluntary and at any stage patients may opt out to pursue any alternative treatment they wish. Once the trial is unblinded patients who received placebo during the trial may be treated with rifaximin if they so wish.

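### The plan describes no way of asking any patient about adverse events, so during dosing the grade 3–4 stopping rule and SAE reporting rest on spontaneous reports

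*Combined protocol and SAP*

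**What the plan says.** Section 10.1 sets three assessment points: day 0 in clinic, then days 26–35 and days 53–63. Patients who volunteer for extra tests return to clinic for the two later points, where the BFI, a breath test and a stool sample are listed. For the others the entry reads "Post treatment evaluation for patients not volunteering for extra tests which can be undertaken in the patients home", and the BFI is the only item under it. Section 7.0 says of the volunteers "We hope to recruit half of the patients in each arm to participate in the extra testing", and of those who decline "they will be tested using the MSKCC BFI alone at the relevant time periods". Between those two statements it adds "All patients will fill out the stool log/diary".

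The diary is weekly. Section 10.1 gives its content: "The questions asked will address range of stools per day, stool formation, flatus, incontinence, ability to completely evacuate". It adds "Patient compliance will also be assessed in the log".

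Two kinds of staff contact are described for patients followed at home. Section 4.2 says "they will be reminded by phone, mail or email to fill out the BFI", and Section 10.1 provides for a physician's call when BFI answers are incomplete or ambiguous.

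The safety rules stand elsewhere. Section 17.1 says "Should patients develop grade 3 or 4 toxicity to the antibiotic treatment, their treatment will be stopped" and that such patients leave the study. Section 13.1 lists a grade 3 or 4 reaction to rifaximin as a reason for removal. Section 17.3 requires SAE reports to the IRB/PB within 5 calendar days.

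**The concern.** A stopping rule, a removal criterion and an SAE deadline all act on events that someone already knows about. The plan says what to do with a severe reaction once it is known, but not how it becomes known. If nobody asks, a reaction during dosing can go unnoticed or surface only after the course has ended. Less severe events are then recorded only when a patient happens to mention them, and any later description of tolerability rests on an unknown fraction of what occurred. Section 11.2 lists reactions that bowel-function questions would not reveal, such as dizziness (13%) and rash (5%).

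**Working it through.** The plan gives no figure on this point, and its power calculation does not bear on it. The check is to list every scheduled occasion on which data are collected or staff are in touch, and see whether an adverse-event question is stated.

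| Occasion | Who | What the plan lists | Adverse-event question stated? |
|---|---|---|---|
| Day 0, clinic (10.1) | All | BFI; breath and stool tests for volunteers | No |
| Weekly diary (9.0, 10.1) | All | Bowel items, compliance, missed doses | No |
| Days 26–35 and 53–63, clinic (10.1) | Volunteers | BFI, breath test, stool sample | No |
| Days 26–35 and 53–63, home (10.1) | Non-volunteers | BFI | No |
| Reminder by phone, mail or email (4.2) | Non-volunteers | Prompt to complete the BFI | No |
| Physician's call (10.1) | Those with unclear BFI answers | Clarifying the answer | No |
| Return of container and unused drug (9.0) | All | Mailing back | No |

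**Timing.** Dosing lasts 4 × 7 = 28 days. The first assessment after day 0 opens on day 26, for clinic and home patients alike. The first 26 of the 28 days therefore contain no scheduled visit for anyone. Over the course the diary yields about 28 / 7 = 4 entries, and it is the only scheduled data collection in that period.

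**Who is affected.** The gap covers all 70 planned patients. If half of each arm volunteers, 0.5 × 35 = 17.5, so about 17–18 per arm (about 35 of 70) are followed at home. The other half see a physician at the later points, where an event might come up informally, but no such question is written down for them.

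**What the safety rules presuppose.** Sections 13.1 and 17.1 need an event that is known and graded. No section names a grading scale, a person who asks, or a schedule for asking. Section 17.3 covers onward reporting, including severity and relationship, of events already found. Section 16.3 describes monitoring bodies, which can review only what is collected. Section 14.0 plans no tabulation of adverse events.

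**Follow-up study.** The metronidazole phase is run by phone and mail with the BFI and diary (Sections 4.2 and 10.1), so it has the same gap.

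That detection depends on spontaneous reports is an inference from this absence. Nothing in the documents contradicts it.

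**The case against.** The strongest reply is that the diary form is not in the text available. Section 10.1 says what its questions address without calling the list exhaustive, and the form or the consent material may ask about side effects or tell patients to report them. This stands as a limit: the finding concerns the stated content of the diary. It does not settle the matter, because the plan's text still names no method of enquiry and no analysis of the answers.

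A second reply is that patients are not out of contact. They complete diaries, may be phoned about the BFI and return unused drug; a study assistant is assigned, and institutional monitoring applies. That is true, but none of these is described as an enquiry about adverse events.

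Three stronger readings are tempting, and the documents support none of them.

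- A reader might infer from "they will be tested using the MSKCC BFI alone at the relevant time periods" that home patients are singled out for weaker safety enquiry. The sentence contrasts the BFI with stool and breath testing. The clinic visits list no adverse-event question either, and they fall too late to help during most of dosing.
- A reader might infer bias in favour of rifaximin. Patients and physicians are blinded, only dispensing pharmacists can see assignments (Section 15.3), and volunteers are hoped to be half of each arm. Missed events should be roughly balanced, so sensitivity is lost with no stated reason for a tilt. Section 14.0 also plans no safety comparison that could be biased.
- A reader might try to put a number on the loss. The 14% nausea rate gives 0.14 × 35 = 4.9 patients in the rifaximin arm, and losing half of the events in the home-followed half would remove a quarter of them. But the reporting fraction is pure assumption. The 14% also comes from a list that includes ascites and esophageal varices, so apparently from a different population, and it is not placebo-corrected. Likewise, with zero severe events the one-sided 95% upper limit is 1 − 0.05^(1/35) = 8.2% for 35 patients. It is 15.3% for 18 and 16.2% for 17, but using the smaller numbers supposes that clinic patients are asked and that home patients contribute nothing. The documents say neither.

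**Conclusion.** The point holds for the whole trial. As written, the plan has rules for acting on severe toxicity but no described means of finding it, and the weekly diary is the only scheduled data collection for the first 26 of 28 dosing days. On the text available, the stopping and removal rule and SAE reporting depend on spontaneous reports.

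The conclusion rests on two assumptions: that the diary form matches its description in Section 10.1, and that no other material instructs staff or patients about adverse events. If the form already has such an item, what remains is to say so in the plan and to state how the answers are used.

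The expected consequence is missed or late events and under-counting in both arms. No numerical loss can be derived. The primary BFI analysis is not called into question. The change is nevertheless worth making, because it alters what the trial can detect while patients are taking the drug.

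**What to change.** Unless the form already has one, add a single standard adverse-event question to the weekly diary for every patient. Ask the same question at the day 26–35 and day 53–63 assessments, in the same words for clinic and home patients, and tabulate the answers by arm.

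The parts do different work. Only the diary item can support the existing stopping rule during dosing, because the first assessment falls at or after the end of the course. The questions at the two assessments make the count more complete and enquiry equal across follow-up routes. Section 10.1 says a completed log may be posted or emailed but does not clearly say that each week's entry is sent as it is filled in. The plan should state this and say who reads entries on arrival, since an answer read after the course cannot inform stopping. No dose, stopping criterion or other clinical rule changes.

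The cost is one diary line, one question at contacts that already exist, and some staff time to read the answers. The diary becomes slightly longer, and more minor events will be recorded.

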8.1 PRETREATMENT EVALUATION

- Routine clinic evaluation at MSKCC ≤ 12 months of beginning the trial.
- Serum beta-HcG levels for pre-menopausal women (last menses within one year) ≤ 2 weeks.

9.0 TREATMENT/INTERVENTION PLAN

The planned treatment during this trial will be the administration of the antibiotic rifaximin 400mg bid for 4 weeks or a placebo bid for 4 weeks to patients with bowel dysfunction. Both rifaximin and placebo will be prepared in identical capsules by the research pharmacist at MSKCC and distributed to the outpatient pharmacies. Following registration to the trial patients will be given a prescription for the trial, which they will be able to fill out at one of the MSKCC satellite center outpatient pharmacies. Patients will be instructed to take their treatment at the same time in the morning and the evening. Any missed doses will be recorded in the stool diary/log. Once treatment has been completed patients will be asked to mail back the treatment container along with any unused medication.

Once the trial has been completed and patients have been unblinded, patients may elect to be treated with Rifaximin if they so wish.

10.1 EVALUATION DURING TREATMENT/INTERVENTION

Pre-treatment intervention & evaluation all undertaken in an outpatient clinic (day 0)

- MSKCC BFI (for all patients)
- Breath test (for patient volunteers)
- Stool Sampling (for patient volunteers)

Treatment with 400 mg rifaximin bid x 4 weeks or placebo bid x 4 weeks.

Post treatment evaluation at an outpatient clinic, for those patients who volunteered for extra testing. (days 26 - 35 and days 53 – 63)

- MSKCC BFI
- Breath test
- Stool Sampling

Post treatment evaluation for patients not volunteering for extra tests which can be undertaken in the patients home during the following periods. (days 26 - 35 and 53 – 63)

- **MSKCC BFI**

All patients will be required to fill out a weekly stool log/diary for the duration of the trial. There are questions in the log/diary to assess patient compliance also.

One to twenty-four months following completion of the phase III trial patients will be offered a 3 week course of metronidazole. They will then be assessed again using the BFI at pretreatment and at 0-1 and 4-6 weeks post-treatment. (21-30 days and 49 – 63 days following starting metronidazole)

MSKCC BFI

The MSKCC BFI is a validated instrument in the assessment of bowel function following rectal cancer surgery over a 4 week period.[5] It consists of 18 items to which patients respond using a 5-point Likert scale, ranging from Always to Never. There is a summary score, and three subscales with good internal consistency (Frequency ($\alpha=0.75$), Dietary ($\alpha=0.78$), Urgency ($\alpha=0.79$)) and test-retest reliability (total score =0.84, Frequency=0.74, Dietary=0.62, Urgency=0.87). The instrument has demonstrated discriminant and construct validity. It is written at a grade 8 reading level, and takes 5-10 minutes to complete. The BFI if filled out at home can be emailed or mailed back to the investigator where they will be stored on a secure database and a locked drawer. Should there be any incomplete or ambiguous answers a follow up phone call will be made by one of the consenting physicians to clarify the answer. However in a prior trial by the Co-PI ([name] 06-151), of the 125 patients who answered the BFI on multiple occasions less than 5 items per question were missing or filled out inadequately.

Breath Test

Methane and hydrogen breath testing is currently the best non-invasive way of assessing small bowel bacterial overgrowth.[22] The test takes 1 hour and can be taken in the outpatient clinic. The patient must fast at least 12 hours prior to starting the test. The patient takes a baseline breath and exhales into a container. He/she then ingests a quantity of lactulose. If there is overgrowth of bacteria in the small intestine the sugar is not absorbed but is instead fermented by the bacteria in the gastrointestinal tract producing hydrogen and methane. The human body does not endogenously produce either of these gasses. These gasses can then be detected in the breaths of patients indicating bacterial overgrowth in the small bowel. Subsequent breaths are then taken at varying intervals up to 90 minutes from the initial ingestion of the sugar and are assessed for methane and hydrogen levels. The samples will be analyzed at Metabolic Solutions Incorporated®, a commercial laboratory.

Stool Sampling

Memorial Sloan Kettering Cancer Center
[name]
[name]

Stool samples will be taken during the outpatient visits. Patients can submit a sample by defecating into a container or a sample can be taken by gentle rectal examination. The samples will be collected in the outpatient setting and frozen at -80 degrees Celsius. DNA will be extracted using commercial kits (Qiagen®). Bacterial culture has proven to be unreliable as a quantitative measure of fecal content as only a tiny minority of fecal bacteria will survive in culture. As such we plan to quantify fecal bacteria using real time quantitative PCR for the gene for 16s ribosomal RNA as previously described.[23] This gene is present in all bacteria and has both conserved and variable domains. For quantification of total fecal bacteria, PCR primers amplifying the conserved domain will be used and the PCR product will be measured using the Syber Green method.

To evaluate the spectrum of fecal bacteria, a PCR plus 454 pyrosequencing technique optimized by one of the Co-Investigators ([name]) will be used. The conserved and variable domains of the gene 16S ribosomal RNA will be amplified as one PCR product using previously described primers. From this product, the variable domain will be analyzed using 454 pyrosequencing technique. Microbial complexity will be determined and comparisons between samples will be performed using UniFrac and Principal Coordinates Analysis. Approximately 120 species of bacteria will be represented in the various Pyrosequencing primers. The read out of the assay will give a positive fluorescent signal for each bacterial species present in the feces.

Expertise in both quantifying total bacterial load and identifying fecal colonization patterns will be provided by [name] and his laboratory.[24]

Stool Diary/Log

The stool diary/log will allow the investigators to follow trends in bowel function and to assess how long the antibiotic effect lasts. Patients will be asked to fill the diary out once per week (+/- 2 days) on paper or by email before and through the duration of the trial. The questions asked will address range of stools per day, stool formation, flatus, incontinence, ability to completely evacuate. Patient compliance will also be assessed in the log. It will not take longer than 3 minutes to fill out. Once the log is completed it can be posted or emailed back to the investigator where it will be stored on a secure database and a locked drawer.

